Once enrolled into the study, each participant will be initially randomized into one of the two intervention groups: (1) SMS + multi-media page, or (2) Phone call with a peer. For household members, randomization will occur at the family unit and all participants will receive the same intervention. All participants will be asked at the start of the study a vaccine-uptake survey regarding the following: their overall willingness to get vaccinated and willingness to vaccinate their children (if applicable); factors that increase and decrease willingness to vaccinate, and their barriers that inhibited their ability to vaccinate.

Within one week of enrollment, the participant/family unit will receive the first intervention. A study team member will follow-up with the participant(s) to determine any changes in vaccination status at the two-weeks receiving their first intervention. If the participant(s) have no changes in their vaccination status, the participant/family unit will undergo a second round of randomization within one week of this follow-up. The same two interventions will be used, so an

individual will receive *either* a second exposure to the same intervention or the intervention that they did not initially receive. After two weeks of the participant's 2nd randomization, a study team member will follow-up a second time to determine vaccination status. During each follow-up session, a study team will provide the same vaccine-uptake survey to the participant and offer to provide vaccine resources on where to obtain a vaccine for the participants. If a participant receives a vaccine an additional phone call will be performed 4 weeks after their first vaccine dose to assess if they completed the primary vaccination series. Compensation of \$100 will be provided for those individuals consenting to this study. This compensation will be provided in allotments of \$50 after completing the consent document and then \$25 after each randomization. If a participant does not need to be randomized a second time, the second \$25 will be provided when learning of the participant receiving their vaccine.

Assessing Vaccine Strategies

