The primary outcome of this study will be the percentage of individuals who received an initial vaccination within two weeks of a study intervention. Vaccine uptake will be primarily assessed by verbal confirmation of recent vaccination during a follow-up visit with a study team member. We will ask for visual documentation of the vaccine card or receipt that demonstrates the vaccine has been administered. Any participants lost to follow-up will be presumed "Unable to determine." A secondary outcome will be the number of individuals that complete their primary vaccination series within 6 weeks of their first dose.

In addition, data from the vaccine-uptake survey will analyzed for trends in willingness to vaccinate within participants. Changes promoting vaccine willingness could be indicative of an impactful vaccine intervention.

E Statistical Plan

Statistical considerations

Primary analysis

Our primary hypothesis is that the initial strategy of peer counseling will result in the highest vaccine uptake. To test this hypothesis we will use a generalized linear mixed model approach, assuming a binomial distribution and a logit link function. The intervention (peer counseling vs SMS + multimedia website) will be modeled as a fixed effect, and household will be included as a random effect to adjust for within household clustering. As this hypothesis focuses on addressing the best initial intervention, we will include only data collected through the first assessment in this analysis (~ 2 weeks following enrollment). If we find a significant difference (P < 0.05) and the proportion of vaccinated participants is greater in the peer counseling group, then we will conclude that the peer counseling is superior to the SMS + video as an initial vaccination strategy. We will also evaluate whether there is evidence of imbalance between the intervention groups for a variety of covariates including: age, race/ethnicity, sex, zip code, school district, highest education level, vaccine hesitancy, influenza vaccine history, previous COVID-19 illness, household member vaccinated, health insurance type, and perceived COVID-19 risk. If we find some evidence of a difference between the initial intervention groups (P <

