We powered this study to test the primary hypothesis that an initial intervention of peer counseling will result in greater vaccine uptake compared to the SMS + multimedia website intervention. The sample size needed to test this hypothesis was based on pilot data as well as scientific literature on vaccination uptake. One research study estimated an increase COVID-19 vaccine uptake rate of 3.6% with a text reminder treatment compared to a holdout arm that did not receive a reminder^{11C}. Our listening session data from our community members, felt that receiving vaccination information from a peer would be helpful in becoming vaccinated. Additionally, peer counseling has been noted to increase breastfeeding rates in different race/ethnicity groups of at least 15%. For this reason, we estimate that 15% of participants will agree to a vaccine after having a conversation with a peer. Pilot data available for the study population indicated that the median household size was 1, and for the power analysis we assume 1 person per household but in the main analyses we will include a random effect to account for possible clustering at the household level if there is greater than one person per household. The aforementioned estimates from the literature served as our targets, but due to the inherent uncertainty in the application of results from prior studies to different target populations, we estimated the necessary sample sizes for a range of vaccine uptake-rates (Table 1). Based on these estimates we anticipate that a total drop-out adjusted sample size (peer counseling, SMS + multimedia website) ranging from 285 (increase in vaccine uptake of 12%) to 1113 (increase in vaccine update of 5%) would provide a minimum of 80% power to detect the

effect of interest. These sample sizes are attainable as we already have approximately 1000 unvaccinated individuals that we can contact for enrolment. Additionally, we will be adding more school districts to be eligible for testing. Lastly, we will recruit for enrollment beyond just testing as we utilize our community partners to help us with recruitment.

Increase in % uptake of vaccine	Total sample (unadjusted for drop out)	Total sample size + design effect*	Total sample (adjusted for 20% drop out)			
5%	712	890	1113			
7%	416	520	650			
9%	282	353	442			
12%	182	228	285			

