Table 1. Sample size estimates for different scenarios comparing the peer intervention to the SMS + multimedia website intervention. All scenarios assume 80% power and a 3.6% vaccine uptake rate for SMS + multimedia website based on results from Dai et al. 2021. *Design effect assumes an intracluster correlation of 0.50 and an average cluster size of 1.5.

Data management

All testing data are maintained in a secure, password-protected REDCap database. Information collected on paper forms is stored in locked filing cabinets on a restricted-access floor at WUSM. Prior to undergoing testing, participants will complete a HIPAA authorization form and/or informed consent to allow SARS-CoV-2 testing data to be shared with the State of Missouri. All participants are assigned an ID number, and testing information is kept separate from the demographic data. Subjects who test positive are contacted by phone to be given their results. This information will be shared only with the participant unless an informed consent is signed that will allow sharing of their data with the RADx-UP Coordination and Data Collection Center.. Data are stored using HIPAA-compliant encryption to comply with all local, state, and national regulations for health-related data.

Our existing Consortium Data Reporting Unit (CDRU), in collaboration with our data manager, will coordinate the submission of common data element metrics on SARS-CoV-2 testing-related outcomes to the RADx-UP CDCC at Duke University. We will comply with data sharing as mandated by the NIH and follow guidance provided by the CDCC for data acquisition, collection, and curation, including appropriate consent for data sharing and implementation of the schemas proposed under the ABOUT ML effort. The CDRU will also ensure compliance with federal, state, and local requirements and policies for testing, reporting, and surveillance. The CDRU will also work closely with the CDCC to employ a common set of tools to promote collection of comparable data on social determinants of health, including measures from the PhenX Toolkit. Effective implementation strategies for rapid adoption will be disseminated through the CDCC.

We will work collaboratively with the Duke CDCC in reviewing and revising our data collection tools to ensure we are collecting the appropriate CDEs. We will share our data with Duke

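### The sample-size text assumes one person per household, but the totals it quotes carry a 1.25 design effect, which is slightly too small if 1.5 is the plain mean household size

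*Combined protocol and SAP*

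**What the plan says.** All of this is in section E, Statistical Plan, under Sample size estimates, unless stated otherwise.

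- On household size, the text reports: "Pilot data available for the study population indicated that the median household size was 1". It continues that "for the power analysis we assume 1 person per household" and leaves any clustering to the household random effect in the main analyses.
- The same paragraph gives the required totals as "ranging from 285 (increase in vaccine uptake of 12%) to 1113 (increase in vaccine update of 5" percentage points), with at least 80% power.
- The note under the sample-size table reads: "Design effect assumes an intracluster correlation of 0.50 and an average cluster size of 1.5". It also reads: "All scenarios assume 80% power and a 3.6% vaccine uptake rate for SMS + multimedia website".
- The last column is headed "Total sample (adjusted for 20% drop out"). It holds 1113, 650, 442 and 285, which are the totals quoted in the text.
- Section D2, Randomization, assigns members of one household together, as a family unit. Section E, Primary analysis, fits a logistic mixed model with a household random effect.

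**The concern.** There are two separate problems.

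First, the text and the table note give different household sizes for one calculation. One person per household means no clustering and a design effect of 1. An average of 1.5 with an ICC of 0.50 means a design effect above 1. A reader cannot tell which assumption supports the quoted range.

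Second, the simple formula behind the table's factor is exact only when all clusters are the same size. No household can have 1.5 members, so a plain mean of 1.5 forces sizes to vary, and variation raises the design effect. At an ICC as high as 0.50 this is not negligible. At stake is whether the power stated for the primary hypothesis follows from the plan's own inputs.

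**Working it through.** **Inputs.** SMS-arm uptake 3.6%, increases of 5, 7, 9 and 12 points, 80% power, 20% dropout, ICC 0.50 and average cluster size 1.5 all come from the sample-size table and its note. Alpha 0.05 comes from Primary analysis ("If we find a significant difference (P < 0.05")). Sidedness and allocation ratio are not stated ("each participant will be initially randomized into one of the two intervention groups"). Two-sided and 1:1 are assumed here because they reproduce the table.

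**1. Reproduce the plan's figures.** With unpooled variance, n per arm = (1.960 + 0.842)² × [p0(1−p0) + p1(1−p1)] / d².

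- 5 points: 7.849 × (0.0347 + 0.0786) / 0.0025 = 355.7, rounded up to 356 per arm, total 712.
- The same steps give 416, 282 and 182 for 7, 9 and 12 points. The base column is reproduced exactly.
- Design effect: 1 + (1.5 − 1) × 0.50 = 1.25, giving 890/520/353/228.
- Dropout, dividing by 0.8: 1113/650/442/285. The quoted range is reproduced exactly, and it contains the 1.25.

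**2. The text's assumption (one person per household, design effect 1).** Base totals divided by 0.8 are 890/520/353/228. At the stated 1113, the analysed number per arm is 1113 × 0.8 / 2 = 445.2. The standard error is √(0.1133/445.2) = 0.01595, and 0.05/0.01595 − 1.960 = 1.174, so power is about 88%.

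**3. The table's assumption, with 1.5 as the plain mean size.** Let m be household size.

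- Standard formula: 1 + (E[m²]/E[m] − 1) × ICC.
- Optimal weighting, closer to a mixed model: E[m] / E[m/(1 + (m−1) × ICC)].

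For whole-number sizes with mean 1.5, both are smallest at half singles and half pairs. That mix is also consistent with a median of 1.

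- Standard: E[m²] = 0.5 × 1 + 0.5 × 4 = 2.5, so 1 + (2.5/1.5 − 1) × 0.50 = 1.333.
- Weighted: 1.5 / (0.5 × 1 + 0.5 × 2/1.5) = 1.5/1.1667 = 1.286.

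**4. Consequence.** Totals are rounded up at each step, as in the plan. Power is for the 5-point row at 1113.

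| Design effect | Total, 5 points | Total, 12 points | Power at 1113 |
|---|---|---|---|
| 1.00 (text) | 890 | 228 | about 88% |
| 1.25 (table) | 1113 | 285 | 80% |
| 1.286 (weighted) | 1145 | 293 | about 79% |
| 1.333 (standard) | 1188 | 304 | about 77.5% |

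Relative to 1113, the extra requirement is 1145/1113 = 2.9% more or 1188/1113 = 6.7% more.

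**The case against.** **The sentence may describe only the base column.** The table shows the design effect in its own column with a footnote, so nothing is hidden, and the table asks for more participants than the text's assumption would. The point about disclosure and direction stands. It does not remove the contradiction: the sentence refers to the power analysis as a whole, and the range quoted in that paragraph is not the base column.

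**Using the mean cluster size in the simple formula is a common planning approximation.** This is fair, and 1.25 is computed correctly from the stated inputs. The gap is also small beside other uncertainties. Pooled variance would give base totals of 718 instead of 712 and 188 instead of 182. The ICC of 0.50 has no stated source, and at about 0.43 the half-and-half mix gives 1.25 under weighting. The planned random effect also makes 1.286 the closer figure, so the milder shortfall is the more relevant one.

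**A reader might infer that 1.25 is too small for any real mix of households.** The documents do not support that.

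- If 1.5 is a participant-weighted mean, E[m²]/E[m], the standard formula gives exactly 1.25.
- If 1.5 is the mean at enrolment and 20% of individuals drop out independently, half singles and half pairs becomes 56% analysed singles and 32% analysed pairs, with the rest lost entirely. The design effect is then 1.267 (standard) or 1.216 (weighted). Because family follow-up runs through one designated member, loss of whole households is also plausible, and the documents do not settle this.
- A population with fewer pairs also fits a median of 1. With 20% pairs the standard formula gives 1.17, but the mean is then 1.2, not 1.5.

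**A reader might also infer a much larger loss from skewed sizes.** For example, 75% singles and 25% households of three also average 1.5 and give 1.50 by the standard formula. That mix is only an illustration, since the documents report a median and no distribution.

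**Conclusion.** The inconsistency between text and table is certain. The understated design effect holds if 1.5 is the plain mean size of analysed households and the ICC is 0.50. In that case the smallest possible design effect is 1.286 to 1.333, and power at the stated totals is about 79% to 77.5% instead of 80%.

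It would be wrong to conclude that the 80% claim fails whichever description is right. Under the text's one-person assumption power is about 88%, which satisfies it. The claim falls short only under the table's assumption, and at the minimum the shortfall is modest. This is a flaw in the sample-size justification that should be corrected; it does not show that the trial is materially underpowered.

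**What to change.** 1. Correct the one-person sentence so that it matches the table.
2. State whether 1.5 is a plain or participant-weighted mean, and whether it counts enrolled or analysed members.
3. Report the pilot mean and coefficient of variation (CV) of household size, and compute the design effect as 1 + ((1 + CV²) × mean − 1) × ICC. As a check, half singles and half pairs has CV² = 0.25/2.25 = 0.111, which returns 1.333. The weighted version could be given beside it, since the primary model has a household random effect.
4. Restate the power at the stated totals, or restate the table sizes.

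The cost is a recalculation, a few changed words and probably a slightly less favourable stated figure. No extra participants are needed if the power is restated.

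### The 3.6% text-message figure is an increase over a holdout arm in the text but the absolute SMS-arm rate in the sample-size table; its derivation is not shown, and the stated 80% power is conditional on it.

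*Combined protocol and SAP*

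**What the plan says.** All of this is in section E, under Sample size estimates.

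- **Text.** The required size "was based on pilot data as well as scientific literature on vaccination uptake". For text messaging, the cited study (reference 11) found "an increase COVID-19 vaccine uptake rate of 3.6% with a text reminder treatment compared to a holdout arm" that received no reminder.
- **Table 1 note.** "All scenarios assume 80% power and a 3.6% vaccine uptake rate for SMS + multimedia website", credited to that same study.
- **Peer arm.** The text reports that "peer counseling has been noted to increase breastfeeding rates in different race/ethnicity groups of at least 15" percent, and for this reason: "we estimate that 15% of participants will agree to a vaccine after having a conversation with a peer".
- **Uncertainty.** Because results may not carry over between populations, "we estimated the necessary sample sizes for a range of vaccine uptake-rates (Table 1"). Its rows are increases of 5, 7, 9 and 12 points, with final totals of 1113, 650, 442 and 285.
- **Power.** These totals "would provide a minimum of 80% power to detect" the effect of interest.
- **Clustering.** The text says that "for the power analysis we assume 1 person per household". The table multiplies by a design effect based on an average cluster size of 1.5 and an intracluster correlation of 0.50.

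**The concern.** The text's comparison with a holdout arm makes 3.6% a difference between two arms. The table note makes it the level in one arm. A percentage-point difference equals the level only if nobody in the holdout arm was vaccinated, and the plan gives no holdout rate.

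The plan also does not show how 3.6% became an absolute rate over two weeks, which is the window of the primary outcome. Pilot data are invoked, but the only pilot figure reported is the median household size. The peer-arm 15% was likewise carried over from a reported increase, in another behaviour.

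The text announces a range of uptake rates. The table varies the increase, and so the implied peer rate (8.6% to 15.6%), but never the SMS rate. The input whose meaning is unclear is thus the one without a sensitivity analysis. At stake is what a null primary result would mean: its interpretation depends on a power statement that rests on this input.

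**Working it through.** **Inputs.** From section E: SMS rate p1 = 0.036; increases d = 0.05, 0.07, 0.09, 0.12; power 80%; significance level 0.05; design effect 1 + (1.5 − 1) × 0.50 = 1.25; dropout 20%. Two-sided testing and 1:1 allocation are not stated. I assume both, and they reproduce the table.

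**Step 1: reproduce Table 1.** With p2 = p1 + d,

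n per arm = (1.96 + 0.8416)² × [p1(1 − p1) + p2(1 − p2)] / d².

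For the 5-point row: 7.849 × (0.034704 + 0.078604) / 0.0025 = 355.7, so 356 per arm and 712 in total. Then 712 × 1.25 = 890, and 890 / 0.80 = 1112.5, rounded up to 1113. The four rows give:

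- unadjusted: 712, 416, 282, 182
- with design effect: 890, 520, 353, 228
- with dropout: 1113, 650, 442, 285

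All 12 cells match. The arithmetic is right, and 3.6% entered it as an absolute rate.

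**Step 2: vary the SMS rate with the percentage-point difference fixed.** The effective n per arm at a stated total N is N × 0.80 / 1.25 / 2, and

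power = Φ( d / √{[p1(1 − p1) + p2(1 − p2)] / n} − 1.96 ).

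Example, 5-point row at SMS 5.6%: n = 1113 × 0.80 / 1.25 / 2 = 356.16; standard error = √[(0.052864 + 0.094764) / 356.16] = 0.02036; 0.05 / 0.02036 = 2.456; Φ(2.456 − 1.96) = 69%. SMS rates other than 3.6% are assumptions.

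| SMS rate | 5 points, N=1113 | 7 points, N=650 | 9 points, N=442 | 12 points, N=285 |
|---|---|---|---|---|
| 2% | 90% | 89% | 88% | 86% |
| 3.6% | 80% | 80% | 80% | 80% |
| 5.6% | 69% | 71% | 72% | 73% |
| 8.6% | 57% | 60% | 62% | 64% |

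The largest SMS rate that keeps 80% is 3.61, 3.62, 3.67 and 3.66% in the four rows. With a design effect of 1 (one person per household) it is 5.25, 5.56, 5.91 and 6.34%.

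**Step 3: hold the odds ratio fixed instead.** Each row implies OR = [p2 / (1 − p2)] / [0.036 / 0.964], that is 2.52, 3.17, 3.86 and 4.95. Applying these to other SMS rates, with the same totals and design effect 1.25, gives power of about 57% at SMS 2%, 93% at 5.6% and 98% at 8.6%, nearly the same in every row. The direction is opposite to step 2.

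**Step 4: the plan's own targets.** At 15% against 3.6% (11.4 points) and design effect 1.25, power at the four totals is 100, 98, 92 and 77%. With peer uptake kept at 15% and SMS at 5.6% (9.4 points), it is 99, 89, 75 and 56%.

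**The case against.** **The two descriptions may agree.** The sentence in the text is ungrammatical. It could mean an increased uptake rate, equal to 3.6%, in the texted arm. The table note would then be consistent with it. This cannot be excluded, so the contradiction is the natural reading but not a certain one. The wording needs repair under either reading.

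**The condition is printed.** A reader might infer that 80% power is claimed without any condition. It is not: the 3.6% assumption stands in the note under the table. What is missing is a sensitivity analysis on it.

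**A source is given.** A reader might infer that the 3.6% has no basis. The plan cites a study, so the supportable gap is narrower: the documents do not show how an absolute two-week rate was derived from it.

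**Harm depends on the effect scale.** A reader might infer that a higher SMS rate must cost power. Table 1 is built on percentage-point differences, and on that scale it does. The primary model is logistic, however, and at a fixed odds ratio a higher rate helps (step 3). The plan does not say which quantity would stay constant.

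**There is slack.** The range of totals was given because of acknowledged uncertainty, the design effect is a cushion if most households contribute one person, and power is high at the plan's own targets for the larger totals. All of this stands. At those same targets, though, the smallest total gives 77% with the design effect of 1.25.

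**Conclusion.** The point holds as an unclear input whose derivation is not shown, and it should be fixed. On the natural reading, the text and the table note describe 3.6% differently, and the table keeps it constant in every row. For the listed percentage-point differences and a design effect of 1.25, the minimum of 80% is a minimum only up to an SMS rate of about 3.6%. Power is 69 to 73% at 5.6%, 57 to 64% at 8.6% and 86 to 90% at 2%. At fixed odds ratios the ordering reverses.

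It is tempting to conclude that the trial is underpowered. The documents do not support that: they give no holdout rate, do not indicate whether the true SMS rate lies above or below 3.6%, and name a range of totals. The estimand, the test and the randomization are unaffected.

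These figures rest on a two-proportion normal approximation, two-sided 0.05, 1:1 allocation and 20% dropout. They are not simulations of the planned mixed model.

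**What to change.** 1. Describe 3.6% the same way in the text and in the Table 1 note.
2. State the assumed absolute two-week uptake in the SMS arm and how it was derived.
3. Extend Table 1 to SMS rates on both sides of 3.6% (for example 2%, 5.6% and 8.6%), and say whether the percentage-point difference or the odds ratio is held fixed.
4. Replace the minimum-power statement with the power or detectable difference at the intended total, conditional on the SMS rate and design effect.
5. As a minor wording point, reconcile the assumption of one person per household with the design effect of 1.25. The table already takes the conservative side.

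The cost is a recalculated table and a few sentences. Design, test and enrolment do not change. The downside is a possibly less favourable stated power.
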